subtopic that meets their need for that week's focus (Women can select the same short-term goal up to two times during weeks 1-10 and two times during weeks 11-20.) Then, they will visualize and describe WHAT the week's goal is, WHY it is important, WHEN, WHERE, and with WHOM it will take place, and HOW it can be accomplished, all of which enhance prospective memory, thus enabling individuals to carry out the plan to reach the goal.¹³¹ Related to HOW, they will be asked to view an example with three specific detailed steps to achieve their chosen goal. *Step I. Use open-ended questions to ask themselves, thus to raise awareness of their current life situations/challenges (e.g., How often do I eat junk foods?). Step II. Take specific steps to overcome the challenges to achieve the chosen goal* (e.g., pay attention to foods I eat and how much I eat). *Step III. Record ways to reward themselves without using foods* (e.g., smile and tell myself, “Wow, I am proud of myself of eating less junk food and being mindful what I eat, each time I follow through my plans”). After that, participants will visualize and describe their three steps (by typing) to accomplish the chosen goal. Next, they will repeat the same process for a second short-term goal for the week. **Motivation.** they will visualize and use the dropdown menus to select (or type in a box) (1) their three most important challenges (e.g., I don't have the willpower) in implementing their steps to accomplish each of the two chosen goals for the week, (2) three potential solutions to overcome each chosen challenge and (3) benefits of overcoming the challenges. Phase I concludes with a summary of the participant's motivation, emotion and cognition. **Participants will be encouraged to accomplish their two chosen goals within the next few days and mentally rehearse their “identified steps” two times daily because rehearsal increases effectiveness of GOEFT on the chosen goals.**¹³²

Part II (weekly days 5-7, 5 min/week): Evaluation of goal progress with feedback. After implementing steps to achieve both chosen goals, they will log into the intervention website and use the

dropdown menus to evaluate their progress on accomplishing their short-term goals, identify tips that proved helpful, recognize short- and long-term benefits of accomplishing the chosen goals, and rate progress on the four long-term intervention goals and three chosen personal values. They will receive feedback to their response for each evaluation component (e.g., short-term goal). Part II concludes with a summary of goal progress with feedback.

Individual coaching session via zoom (15 min/call, 10 calls). Participants will receive a call within 1-2 days after they complete the Part I intervention activities. All coaching session will be either video or audio recorded (per participants' preference) with participants' permission. Participants will be informed that the recording will be transcribed and be used to refine the individual coaching session for future studies. During each call, the research will listen empathetically and use open-ended questions asking participants to visualize and describe how the week's goals fit with their personal values, thereby supporting their motivation (**autonomous motivation**).¹³³ Next, participants will be asked to visualize and describe how they will accomplish the goal(s) – what specific steps they will take. Then, the research staff will assess the specificity of the steps and reinforce or help modify the plans (**emotion and cognition**). Finally, participants will be asked to visualize and describe barriers to implement plans and strategies to overcome barriers. The research staff will assist with problem solving as needed (**self-efficacy**). We will keep IPC attendance records. **Fidelity.** [name] and each research will listen to a random 25% of the audio recordings monthly and use the fidelity checklist to assess protocol adherence, strengths, and reasons for deviations.

Intervention adherence. Each week, participants will receive up to three prescheduled text reminders via their smart phone to engage in the week's intervention activities (until they complete). If women have not completed all activities after seven days, the RA will call and ask them to complete the activities that they have missed and ask reasons for nonadherence. When a woman expresses interest in quitting some aspects of the intervention activities, we will assess barriers to adherence, brainstorm strategies to overcome barriers, and offer options to reduce intervention adherence burden. We will keep intervention adherence log.

E. Internal Validity

Feasibility of recruitment, retention, intervention adherence and acceptability (Aim 1). We already plan to track *recruitment and retention* activities. *Intervention adherence.* The web will track and capture details about all activities (e.g., number of logins and amount of and type of contents used). We will also ask intervention participants about motivation and barriers preventing them from using the web. *Acceptability.* We will assess acceptability by asking participants to evaluate the usefulness of with each intervention component, e.g., personal values, using 5 Ws and H, and rehearsal. Lessons learned and results of this aim will be used to refine our future R01, e.g., recruitment and intervention.

Measures (See above and File Name: Study Survey. shown above). [name] will use the NHANES anthropometric manual¹³⁴ to train the data collectors (unaware of participants' group assignment) on measuring BW until we reach inter-rater reliability of $\geq 95\%$. Self-reported data will be collected online using password-protected security-ensured Research Electronic Data Capture (REDCAP).

F. Statistical analysis

Statistical analysis-need to consistent with hypothesis. We will use descriptive statistics to examine variable distributions, check for outliers, and summarize sample characteristics. Bivariate tests (T-test and Chi-square) will be used to compare sample characteristics between the two study groups. Congruent with the RCT nature of the design, we will conduct intent-to-treat analysis. **Aim 1.** We will (1) conduct content analysis to analyze recruitment/enrollment, retention and intervention adherence logs to identify successful strategies used, (2) review quality of steps generated to achieve goals (using a scoring system), and (3) perform descriptive statistics. We will use the following criteria to determine feasibility: 30% of women screened will meet the study criteria and 8-9 women enroll monthly (recruitment); 75% of consented women will enroll (randomization); 80% women will have measured body weight at T3 (retention). Also, 85% of women will

complete ≥ 12 weekly intervention activity with $\geq 80\%$ weekly activities completed; 75% of women will be able to generate good quality of steps to achieve their chosen goals; 80% will use the pre-written goals instead of type in (intervention implementation). **Aim 2**, we will first use descriptive statistics and trend plots to summarize and visually compare the weekly gestation weight gain over time. Mixed-effects linear modeling will be used to model the weekly GWG as a linear function of treatment (intervention vs. usual prenatal care care), time, and treatment by time interaction. From the model, we can derive estimates of the time-averaged weekly gestational weight gain for each group, the between-group difference in weekly gestational weight gain at each time point and adjust for within-subject clustering from repeated measures and covariates (e.g., race). We will use logistic regression to estimate the between-group (intervention vs. usual care) difference in the probability of having a binary outcome (for example, excessive gestational weight gain, gestational hypertension, new born body weight), adjusting for covariates (e.g., race). **Aims 3 and 4**, mixed-effects linear modeling will be used to model each continuous outcome (dietary intakes, PA, and psychological eating for Aim 3; motivation, emotion and cognition for Aim 4) as a linear function of treatment, time, and the treatment by time interaction. The intervention effects will be estimated by between-group comparisons of change in the outcome (e.g., healthy lifestyle behaviors) from baseline. Again, we will adjust for within-subject clustering from repeated measures and covariates (e.g., race) in the mixed-effects regression models. **Missing data**. We will carefully examine the pattern of missing data and conduct appropriate multiple imputation if missing at random is indicated. The mixed-effects modeling allows for missing at random. If missing not at random exists, pattern mixture modeling will be used. Sensitivity analysis will evaluate the robustness of study findings without multiple imputation vs. those with imputation or from pattern-mixture modeling.

Zoom IRB Boilerplate:

Zoom is a secure, user-friendly, cloud-based enterprise videoconferencing service that Ohio State University implemented in 2018. Zoom is accessible to faculty and staff at all Ohio State campuses via <https://carmenzoom.osu.edu> .

This multifaceted video and audio conferencing system supports video and audio conferencing across multiple platforms, including room systems, mobile devices, desktops and telephones.

The Zoom platform at Ohio State University has two main features: Zoom meetings and Zoom webinars.

Designed to support collaboration, Zoom meetings support up to 300 video participants. By default, any participant in a meeting can share their video and audio and utilize the chat feature to exchange messages with participants. The meeting host controls all meeting features, which include mute/unmute participants, screen sharing, recording options, video sharing, remote screen control and participant annotation. Annotation allows participants to draw and highlight on the screen share. Zoom webinar provides access for up to 300 view-only attendees and features live question-and-answer, polling, registration and post-webinar reporting.

Ohio State University Zoom offers both local recording and cloud recording and has a storage capacity of 270 days for recordings. Cloud recording includes an option to produce an audio transcript for a meeting or webinar. The transcript is saved to the cloud as a separate .vtt text file, and the host can elect to display the transcript text within the video itself, similar to a closed-caption display.

Zoom is accessed via Ohio State's single sign-on solution, which provides an environment in which users can authenticate/log in at one time to a central server and connect with web-based services. Meeting security best practices such as waiting lobby, inability to join before host, disabling of sharing for participants, and disabling annotation by participants by default have been implemented.

III. Bibliography

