Research Protocol

Using mental imagination to prevent excessive gestational weight gain in overweight and obese pregnant women

I. Objectives

1. To determine feasibility of the goal-oriented intervention: recruitment, randomization, retention, and intervention implementation.
2. To investigate the potential efficacy of the intervention on gestational weight gain (primary outcome) and maternal and birth outcomes (secondary outcomes: gestational diabetes, gestational hypertension, mode of delivery, length of labor, apgar score, new born body weight, and premature baby).

Primary hypothesis. A higher proportion of intervention participants will have healthy gestational weight gain than the usual prenatal care participants

Secondary hypothesis. A lower proportion of intervention participants will have gestational diabetes, gestational hypertension, cesarean delivery, premature birth, longer duration of labor, unhealthy birth weight (>4000 or < 2500 grams), premature birth, and APPGAR score ≤ 3 than the usual prenatal care participants.

3. To investigate the potential impact of the intervention on lifestyle behaviors: diet (caloric, fat, sugary drink, fruit and vegetable intakes) and physical activity (walking steps and energy expenditure).

Hypothesis 1. A higher proportion of intervention participants will eat healthier than the usual prenatal care participants.

Hypothesis 2. A higher proportion of intervention participants will have more walking steps and higher energy expenditure than the usual prenatal care participants.

4. To investigate the potential intervention effects on motivation (autonomous motivation, self-efficacy, consideration of future, happiness, and hope), emotion (emotion control, stress, and depressive symptoms), cognition (executive function and impulsiveness) and psychological eating (cognitive restraint eating, emotional eating, overeating and eating out of boredom)

Hypothesis 1. A higher proportion of intervention participants will have higher motivation and self-efficacy, better emotion, higher cognition, and lower psychological eating than the usual prenatal care participants.

[figure not shown]
II. Background and Rationale

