Feasibility. We will use our tracking records to assess recruitment, randomization and retention. To assess intervention implementation, we will extract data from our study web site that will track and capture details about all activities (e.g., amount of and type of activities completed and % of participants used type in box). We will record the attendance of individual coaching session. Intervention participants will report their motivation and barriers preventing them from engaging in the intervention activities and evaluate the usefulness of with each EFT intervention component. We will also use semi-structure interview questions (up to 20 minutes/an individual interview via zoom) to ask participants to evaluate the intervention. We will use website tracking data, individual coaching session, and results of phone interview to revise the intervention contents for a future large scale intervention study.

Primary outcome: GWG (in lbs). Body weight or gestational weight gain will be extracted from participants' electronic health record.

To compute weekly GWG, we will subtract the measured weights between two adjacent time points (T2 vs. T1; T3 vs. T2) then divide by the number of weeks between the two time points. The IOM recommends that overweight women (BMI 25.0-29.9) be limited to total GWG of 15-25 lbs and obese women (BMI ≥ 30.0) to 11-20 lbs.⁹ To compute the total GWG, we will subtract the self-reported pre-pregnancy weight from weight measured at T3. A woman will be identified as having excessive gestational weight gain if her total gestational weight gain exceeds the Institute of Medicine's criteria.

Secondary outcomes: gestational diabetes, gestational hypertension, mode of delivery, length of labor, apgar score, new born body weight, and premature baby will be accessed by [name] (Co-I) or research staff from the participants' electronic health record.

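### Length of labor is hypothesised as a proportion with no threshold, and the Aim 2 analysis names no model that would use the duration itself

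*Combined protocol and SAP*

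**What the plan says.** Section C (Measurement/Instrumentation) lists labor as a duration to be taken from the electronic health record: "Secondary outcomes: gestational diabetes, gestational hypertension, mode of delivery, length of labor, apgar score, new born body weight, and premature baby". It gives no unit, no start or stop point and no category.

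In section I (Objectives), the secondary hypothesis turns labor into a yes/no outcome: "A lower proportion of intervention participants will have gestational diabetes, gestational hypertension, cesarean delivery, premature birth, longer duration of labor". The same sentence gives numerical limits for two neighbouring outcomes, "unhealthy birth weight (>4000 or < 2500 grams), premature birth, and APPGAR score ≤ 3", but none for labor.

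In section F (Statistical analysis), Aim 2 has two models. One is for weight gain: "Mixed-effects linear modeling will be used to model the weekly GWG as a linear function of treatment". The other is for binary outcomes: "We will use logistic regression to estimate the between-group (intervention vs. usual care) difference in the probability of having a binary outcome". The examples attached to the second are "for example, excessive gestational weight gain, gestational hypertension, new born body weight". Labor appears under neither. For Aims 3 and 4 the section states that "mixed-effects linear modeling will be used to model each continuous outcome" and lists the outcome domains covered.

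**The concern.** To test the labor hypothesis as worded, the analyst needs a threshold that the plan does not supply. To analyse the hours instead, the analyst needs a model that Aim 2 does not supply. Either way, a decision that can change the result stays open until data exist.

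Two things are at stake. The first is information: replacing a measured duration with long/not long discards data the trial already holds, in a sample of 72 women at most. The second is the free choice of cut, since different cuts can lead to different conclusions.

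The pilot status does not remove this. The sample size paragraph says that point estimates, effect sizes and confidence intervals will inform the full-scale trial. An odds ratio at an unstated cut is hard to carry into that design.

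**Working it through.** **The plan's own figure.** The only power statement is for weekly GWG (section B, Sample size/power): difference 0.33 lb, SD 0.55 lb, correlation 0.7 between two measures, 36 per arm, two-sided 0.05.
- SD of the mean of two measures: 0.55 × √((1 + 0.7)/2) = 0.507 lb.
- Standard error of the difference: 0.507 × √(2/36) = 0.1195.
- Power: Φ(0.33/0.1195 − 1.96) = Φ(0.80) = 78.8%, or 77.7% with the noncentral t. The plan states 80%.
- Enrolment: 72/(1 − 0.20) = 90, as stated.

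So the figure reproduces to within about 2 points. It says nothing about labor, which is measured once and has no SD, effect size or power in the documents.

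**Assumptions for labor.** Standardized effect d from 0.2 to 0.6 (0.6 is borrowed from weekly GWG). Normality on the analysed scale, for example log hours. Two-sided 0.05. Either 36 women per arm with a labor duration, or 25 per arm to allow for women who never labor. The 25 is assumed; the documents give no rate.

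**Formulas.**
- Full scale: two-sample t test, noncentral t with 2n − 2 degrees of freedom and noncentrality d√(n/2). At d = 0.6 and n = 36 this is 0.6 × √18 = 2.55, giving 70.9%.
- Cut at pooled percentile q: solve ½Φ(c − d/2) + ½Φ(c + d/2) = q for c. The shares above the cut are 1 − Φ(c − d/2) and 1 − Φ(c + d/2). At d = 0.6 these are 0.618 vs 0.382 at the median and 0.343 vs 0.157 at the longest quarter. Power is the exact binomial power of the uncorrected Pearson chi-square test.

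**Results** (power in %, loss in points):

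| n per arm | d | Full scale | Median cut (loss) | Longest quarter (loss) |
|---|---|---|---|---|
| 36 | 0.2 | 13.3 | 9.6 (3.7) | 9.3 (4.0) |
| 36 | 0.3 | 24.1 | 16.2 (7.9) | 15.0 (9.1) |
| 36 | 0.4 | 38.8 | 25.6 (13.1) | 23.0 (15.7) |
| 36 | 0.5 | 55.3 | 37.4 (17.8) | 33.1 (22.2) |
| 36 | 0.6 | 70.9 | 50.6 (20.3) | 44.5 (26.4) |
| 25 | 0.2 | 10.7 | 10.8 (−0.1) | 8.6 (2.1) |
| 25 | 0.3 | 18.0 | 16.2 (1.8) | 12.6 (5.4) |
| 25 | 0.4 | 28.3 | 23.6 (4.7) | 18.3 (10.0) |
| 25 | 0.5 | 41.0 | 32.9 (8.1) | 25.6 (15.4) |
| 25 | 0.6 | 54.7 | 43.5 (11.2) | 34.2 (20.6) |

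Losses are taken before rounding. With 25 per arm the median-cut test has an exact size of about 6.5%, so that column understates the loss. A more extreme cut costs more: at the longest tenth with d = 0.6, power is 31.0% with 36 per arm, a loss of 39.9 points.

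**Choosing the cut afterwards.** In null simulations with 36 per arm and cuts at sample percentiles, one median cut rejects about 3% of the time. The better of two cuts (median, upper quarter) rejects about 8%, and the best of three (adding the upper tenth) about 11%. The best of four (adding the upper third) rejects about 15% or somewhat more, depending on how tied cuts are set.

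**The case against.** The strongest reply is that nowhere do the documents say labor will be dichotomised. Section F does not name labor among its binary examples, and proportion wording does not settle the analysis scale in this protocol. The Aim 3 and 4 hypotheses are also phrased as proportions yet are modelled as continuous, and the primary hypothesis is a proportion while weekly GWG is powered and modelled as continuous. This stands as far as it goes. A reader might infer that the plan commits to a yes/no analysis of labor and nothing else; the text does not support that. But for weekly GWG and for Aims 3 and 4 a linear model is explicitly assigned, and labor gets none. Newborn weight, also a continuous measure, is among the logistic examples.

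The second reply is that any single figure for lost power borrows an effect size from weekly GWG. That is right. A reader might take the d = 0.6 row as the cost; the documents do not support it for labor, and at small effects with 25 per arm the loss nearly vanishes.

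Third, the best scale depends on how intrapartum cesareans and women who never labor are handled. That also stands: the point cannot be claimed to hold whatever rule is adopted, and the fix has to state the rule.

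Finally, this is one of several secondary outcomes in a pilot that disclaims power for effects below 0.6 and promises estimates with intervals. That limits the consequence. Nothing in the plan suggests an intention to search over cuts, so the inflated error rates show what the gap allows, not what is planned.

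**Conclusion.** The concern holds in a limited form. The labor hypothesis has no threshold, the only Aim 2 method that matches it is logistic regression of a binary outcome, and no continuous or time-to-event model is given. Followed literally, the plan dichotomises a duration at a cut that can be set after the data are seen.

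The size depends on assumptions. For d of 0.2 to 0.6, normality on the analysed scale and a cut at the median or longest quarter, the loss is about 4 to 26 points with 36 per arm (20 to 26 at d = 0.6) and about 0 to 21 points with 25 per arm. Choosing among several cuts would push the false-positive rate above 5%, to roughly 8% to 15% for two to four cuts. In a pilot, the lost precision and the open threshold matter more than power as such. The correction is cheap and uses data already being collected, so it should be made.

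**What to change.** In section I, restate this part of the secondary hypothesis as a shorter duration of labor in the intervention group.

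In section F under Aim 2, add that length of labor is analysed on its full scale among women who labor, adjusted for the race stratum, and define which women are included. Linear regression of log hours, reported as a ratio of geometric means with 95% CI, is one suitable choice. If intrapartum cesareans are to be treated as censored or competing events, use a time-to-delivery model instead. Fix the choice before unblinded data are seen. Any percentage with prolonged labor should be descriptive only, at a cut fixed in advance.

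The cost is about one sentence in each section, with no new data. The small downside is that the effect becomes a ratio of durations or a hazard ratio, less familiar than a percentage, and that the analysed women must be defined explicitly.

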A.1. Overweight or obese pregnant women. Nearly 56% of American women aged 20-39 are overweight or obese.¹ These women are at least two times more likely than normal weight women (65-85% for overweight or obese vs. 34% for normal weight) to experience excessive gestational weight gain (EGWG),²⁻⁸ exceeding Institute of Medicine (IOM) pregnancy weight gain guidelines.⁹ EGGW is a serious public health problem because it negatively influences maternal and birth outcomes: gestational diabetes,¹⁰ gestational hypertension,¹¹ cesarean delivery,¹² and fetal macrosomia (birth weight > 4000 gm).^{12,13} EGGW is also a strong predictor of significant postpartum weight retention (retaining ≥ 10 lbs), which is associated with lifelong obesity in mothers¹⁴ and childhood obesity.^{15,16} Pregnancy is a teachable movement for weight management and obesity prevention.¹⁷ Therefore, it is imperative to help overweight or obese pregnant women prevent EGGW.

A.2. Previous lifestyle behavior intervention studies. Healthy lifestyle behaviors (healthy eating and physical activity, **PA**) can prevent EGWG in overweight or obese pregnant women.¹⁸⁻²⁸ Efficacious strategies identified in prior studies involve personalized caloric restriction,²¹⁻²⁵ frequent in-person meeting attendance²²⁻²⁴ or phone counseling^{25,26} and frequent text messages requiring responses.²⁶ Such interventions have limited practicality, scalability, and sustainability due to high participant burden and excessive cost for clinical practice. Also, adherence was problematic,^{22,26,29-31} perhaps because of educational materials and counseling that were prescriptive and not sufficiently flexible or tailored to individuals.³² Moreover, the prior studies paid little or no attention to motivation, emotion and executive function, all of which are crucial for healthy lifestyle behaviors.

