A.3. Conceptual framework (Figure 1). We use future time perspective (FTP) theory (the present anticipation of future goals or personal experience in the past, present and future³³) as a guiding conceptual framework. FTP drives human motivation and behavior in everyday life³⁴ and is crucial to motivate individuals to perform an activity.³⁵ FTP concepts include motivation,³⁶ emotion,³⁴ and cognition.³⁷ Implementation of FTP has focused on episodic future thinking (EFT).³⁷ Our goal-oriented (GO)EFT intervention -- vivid imagination (visualization) of goal-relevant future events in the individual's life³⁸ -- is designed to improve motivation (autonomous motivation, **AuM** and self-efficacy, **SE**), emotion (emotion control, **EC** and stress), and cognition (executive function, **ExF**), all of which promote success in achieving goals for lifestyle behaviors. Key behaviors include healthy dietary intake (less caloric, fat and sugary drink intake and more fruit and vegetable intake) and **PA** (more walking steps and energy expenditure). Key health outcomes are gestational weight gain (**GWG**, *primary outcome*), gestational diabetes (**GDM**), gestational hypertension (**GHT**), cesarean delivery and fetal macrosomia (*secondary outcomes*).

Figure 1. Study Conceptual Framework

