Sample size/power. Our primary outcome variable is weekly gestational weight gain (GWG). A final sample size of 72 women (36 per group, after accounting for 20% attrition from the 90 enrolled) will have 80% power to detect a time-averaged between-group difference in weekly GWG with a medium effect size (standardized between-group difference of 0.6). This effect size is translated to a between-group difference of 0.33 lb in weekly GWG, assuming a common standard deviation of 0.55 lb (or 0.25 kg) based on previous research.²⁷ The power analysis was conducted using mixed-effect linear modeling with a two-sided significance level of 0.05, assuming a correlation of 0.7 between the two weekly GWG measures. Due to the pilot nature of the study, our sample size is not powered to detect smaller effect sizes (<0.6). Nevertheless, we will report point estimates, effect sizes, and 95% confidence intervals. These estimates along with clinical significance will guide the results interpretation and sample size determination for a future full-scale RCT (R01).

C. Measurement/ Instrumentation

All participants will be assessed at ≤ 16 week-gestation (T1), 24-27 week-gestation (T2) and 35-37 week-gestation (T3). Survey data will be collected online using password-protected security-ensured Research Electronic Data Capture (REDCap), a secure web application for building and managing online surveys and databases. Primary and secondary outcomes will be extracted from electronic health record. An incentive of \$40 will be provided for participation in each point of data collection for all measurements.

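### Birth weight above 4000 g and below 2500 g are pooled in the secondary hypothesis, while the framework names macrosomia alone; the two tails could offset each other and no results by tail are planned

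*Combined protocol and SAP*

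**What the plan says.** The combined protocol and SAP describes the birth-weight outcome in several places, and they do not agree.

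- **Section I, Objectives, secondary hypothesis.** A lower proportion in the intervention arm is predicted for "unhealthy birth weight (>4000 or < 2500 grams" (one binary outcome covering both tails). The same hypothesis predicts fewer premature births. Objective 2 above it lists newborn weight with no cut-point.
- **A.1 (background).** Excessive gain is tied to the upper tail only: "fetal macrosomia (birth weight > 4000 gm". Low birth weight is not mentioned.
- **A.3 (conceptual framework).** The listed secondary outcomes end with "cesarean delivery and fetal macrosomia", so here the outcome is macrosomia alone.
- **Section C, secondary outcomes.** Newborn weight is extracted from the health record: "mode of delivery, length of labor, apgar score, new born body weight, and premature baby will be accessed".
- **Section F, Aim 2.** Logistic regression is planned for binary outcomes, with the examples "for example, excessive gestational weight gain, gestational hypertension, new born body weight". No cut-point is restated.

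No section plans separate results for the two tails or an analysis of birth weight in grams. Outside the composite, low birth weight does not appear as an outcome.

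**The concern.** Two problems meet here.

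The first is definition. Sections I and A.3 give different birth-weight outcomes, and section F does not say which one is modelled. The choice could be made after the data are seen.

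The second is interpretation, if section I is followed. The intervention is meant to restrain gestational weight gain. If that also lowers birth weight, fewer babies exceed 4000 g and more could fall below 2500 g. A single proportion adds the two, so a benefit in one tail is offset by a harm in the other. A composite difference near zero could mean no effect or two opposing effects. Under Sample size/power in section B, the plan says that point estimates, effect sizes and 95% confidence intervals will guide interpretation and the size of the full-scale trial, so an uninterpretable estimate matters even where no test is expected to succeed.

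**Working it through.** **The plan's own figure.** The only power statement concerns weekly gestational weight gain: 36 per group "will have 80% power to detect a time-averaged between-group difference in weekly GWG", standardised difference 0.6 (0.33/0.55), correlation 0.7 between two measures, "with a two-sided significance level of 0.05". The SD of the average of two measures is √((1 + 0.7)/2) = 0.922. Power = Φ(0.6/(0.922 × √(2/36)) − 1.96) = Φ(0.80) = 78.8%, close to the stated 80%. Nothing comparable is given for birth weight.

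**Assumed inputs.** The documents give no birth-weight mean, SD, tail rates or expected shift. I assume a normal distribution and a pure downward shift, with central case mean 3400 g, SD 550 g and shift 150 g. The 36 per arm comes from section B.

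**Tail areas, central case.**

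| Outcome | Usual care | Intervention | Change (points) |
|---|---|---|---|
| >4000 g | 1 − Φ(600/550) = 13.8% | 1 − Φ(750/550) = 8.6% | −5.1 |
| <2500 g | Φ(−900/550) = 5.1% | Φ(−750/550) = 8.6% | +3.5 |
| Composite | 18.9% | 17.3% | −1.6 |

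(Changes are from unrounded values.) Macrosomia falls by more than a third and low birth weight rises by about two thirds, yet the composite moves 1.6 points.

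**Range.** For means 3300, 3400 and 3500 g, SDs 500, 550 and 600 g, and shifts 100, 150 and 200 g (27 combinations):

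- above 4000 g falls by 2.6 to 8.1 points;
- below 2500 g rises by 1.3 to 6.7 points;
- the composite changes by −4.6 to +1.5 points. It falls in 18 of the 27, by 1.3 to 4.6 points. At the 3300 g mean it is unchanged (shift 100 g) or rises; full cancellation or reversal occurs only there.

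**If the lower tail moves differently.** Assume macrosomia falls from 15% to 10%, which needs 686 per arm for 80% power when analysed alone. The number needed for the composite depends on low birth weight, assumed 8% under usual care:

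| <2500 g | Composite | n per arm, composite |
|---|---|---|
| 8% to 6% | 23% to 16% | 502 |
| 8% to 8% | 23% to 18% | 1023 |
| 8% to 10% | 23% to 20% | 2943 |
| 8% to 13% | 23% to 23% | no effect to detect |

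Pooling helps in the first row and hurts in the others. The composite alone cannot show which row applies.

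**Precision at 36 per arm, central case.** SE = √(p₁(1 − p₁)/36 + p₂(1 − p₂)/36).

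- Composite: SE 9.1 points, power Φ(1.6/9.1 − 1.96) ≈ 4%.
- Above 4000 g: SE 7.4 points, power Φ(5.1/7.4 − 1.96) ≈ 10%; 95% half-width 1.96 × 7.4 ≈ 15 points.
- Expected counts, usual care versus intervention: 36 × 13.8% ≈ 5 versus 36 × 8.6% ≈ 3 above 4000 g; 36 × 5.1% ≈ 2 versus 3 below 2500 g.

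**The case against.** A reader might infer that the intervention would necessarily push the tails in opposite directions. The documents do not support that. They link excessive gain to macrosomia and say nothing about how low birth weight would respond. The hypothesis of fewer premature births points, if anything, to fewer small babies. The aim is to prevent excessive gain, and the guideline ranges cited in section C have lower limits as well as upper ones. The location shift used above builds opposite movement into every cell, and even then the composite keeps the right direction in most of them. So the supportable word is could.

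A reader might also infer that the plan cannot address macrosomia, or that low birth weight is the one foreseeable harm. Neither follows. A.3 names macrosomia as a secondary outcome, so the text is unreconciled rather than uniformly pooled, and putting the composite into the logistic model requires joining section I to section F. The documents do not list or rank harms of the intervention.

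Finally, this is a pilot powered only for weekly weight gain. Splitting the tails recovers no usable test, and because newborn weight is extracted, either tail can be tabulated later.

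These points lower the severity but do not remove the defect. The definitions still conflict, no breakdown by tail is planned, and separate figures are informative whichever way the lower tail moves.

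**Conclusion.** The point holds as a minor one. The birth-weight outcome is defined in two incompatible ways and modelled without a cut-point, and the pooled version could understate a fall in macrosomia and mask a rise in low birth weight. In the assumed central case a 5.1-point fall in macrosomia appears as a 1.6-point fall in the composite. Exact cancellation or reversal is confined to the lowest mean examined.

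These sizes rest on an assumed normal distribution and a uniform downward shift, none of it from the documents. If low birth weight also falls, pooling costs nothing and may gain precision. The damage is to the estimates and intervals carried into the full-scale trial and to safety reporting. It is not a lost significant result, since no version has useful power at 36 per arm.

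**What to change.** Reconcile the secondary hypothesis (section I), the conceptual framework (A.3) and the Aim 2 analysis (section F):

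- make birth weight above 4000 g alone the birth-weight efficacy outcome, with that cut-point stated in section F;
- report birth weight below 2500 g separately as a safety outcome;
- for each, give counts by arm, the between-group difference and its 95% confidence interval;
- keep the composite, if wanted, as a supplementary summary only.

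Birth weight in grams, adjusted for race, may be added as a supportive analysis. It need not be the main one, because a mean shift does not separate fewer large babies from more small ones.

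The cost is some rewording and one or two extra secondary estimates from data already extracted. Events per tail will be few and the intervals wide, and the report should say so.
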